15.19 SPONSOR REPORTING REQUIREMENTS TO REGULATORY AUTHORITIES

During the course of the study, the Sponsor will report All Adverse Events to the Local Health Authorities, in accordance with the timeframes for reporting specified above.

15.20 BREAKING RANDOMIZATION CODE

In case of an Adverse Event, the code must be broken only in exceptional circumstances when knowledge of the Investigational Product is essential for treating the patient. If possible, a contact should be initiated with the Monitoring Team before breaking the code.

If the blind is broken, the Investigator will document the date, time of day and reason for code breaking in the CRF.

16 STATISTICAL CONSIDERATIONS

16.1 SAMPLE SIZE CALCULATION⁶

Reference to Sanyal AJ, et al. There was a decrease in Alanine aminotransferase level among placebo arm of -20 (U/liter) among the placebo arm while for the active arm, a double of this improvement will be of clinical value. Accordingly, with an alpha error of 5% using one-sided 95% CI of Mann–Whitney U test, a sample power of 80% and an effect size between placebo and lowest active dose of 0.63, a sample of 43 patients for each arm will be required plus an expected drop-out rate of 10% during 9 months' study duration. Thus, a sample of 47 patients per each treatment arm will be appropriate and the total same of the 3 arms will be 141 patients.

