16.4 STATISTICAL ANALYSES

The statistical analysis of this study will consist of reporting of individual data listings, providing descriptive statistics for parameters of interest, and statistical testing of the primary and secondary variables.

The final statistical analyses will be performed when the patients on Heptex and placebo complete 9 months of treatment.

Detailed analysis methods will be provided in the statistical analysis plan.

16.4.1 Descriptive analysis:

- Percent (%) distribution for all categorical variables and mean with (SD) and median (Minimum: Maximum) for continuous variables according their distribution.

16.4.2 Primary analysis:

- The main objectives of this phase II study is to explore the anti-oxidant activity of Heptex as assessed by improvement in serum aspartate aminotransferase (AST) and alanine aminotransferase (ALT) levels by measuring:
- The mean relative change in ALT & AST levels between the experimental arms and the control arm from baseline till end of treatment using T-test (Mann-Whitney test in case of non-parametric data). This analysis will be a comparative analysis and will be done on eligible population of patients without protocol violation and who have at least one treatment dose and an evaluable primary endpoint (AST and ALT).
- Number of patients with normal ALT & AST at end of treatment between the experimental arms and the control arm. The cut-off values of ALT were 0-43 IU/L and of AST were 0-40 IU/L⁸ using chi square (Fischer test for non-parametric data). This analysis will be comparative analysis and will be conducted on the eligible population of patients without protocol deviation, who have at least one treatment dose and an evaluable primary endpoint (ALT and AST).

All tests will be performed on the 5% level of significance.

⁸ Uslusoy H, Nak S, Gülten M, Bıyıklı Z. Non-alcoholic steatohepatitis with normal aminotransferase values. World Journal of Gastroenterology. 2009;15(15):1863.

Procedure for accounting for missing, unused, and spurious data will be explained in the statistical analysis plan.

Any deviation(s) from the original statistical plan will be described in the final report).

16.4.3 Secondary analysis:

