- The mean change in Fib-4 score between the experimental arms and the control arm from baseline till end of treatment using T-test (Mann-Whitney test in case of non-parametric data). This analysis will be a comparative analysis and will be done on eligible population of patients without protocol violation and who have at least one treatment dose and an evaluable primary endpoint (AST and ALT).
- Number of patients experiencing hepatic complications between the experimental arms and control arm at the end of the treatment using chi-square (Fischer for non-parametric data). This analysis will be a comparative analysis and will be done on eligible population of patients without protocol violation and who have at least one treatment dose and an evaluable primary endpoint (AST and ALT).

16.4.4 Exploratory analysis:

- The mean relative change in lipid profile levels between the experimental arms and the control arm from baseline till end of treatment using T-test (Mann-Whitney test in case of non-parametric data). This analysis will be a comparative analysis and will be done on eligible population of patients without protocol violation and who have at least one treatment dose and an evaluable primary endpoint (AST and ALT).

16.4.5 Interim analysis:

- Interim analysis will be performed when all patients complete 6 months of treatment. If a statistically significant difference is observed between placebo and active arm(s), the study will be terminated for the benefit of patients who were randomly assigned to placebo arm and to rapidly disseminate evidence supporting a treatment benefit to the broader community⁹.

⁹Zannad F, et al. Development of Therapeutics for Heart Failure. When to Stop a Clinical Trial Early for Benefit: Lessons Learned and Future Approaches. *Circulation: Heart Failure*. 2012; 5: 294-302. doi: 10.1161/CIRCHEARTFAILURE.111.965707

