19 PREMATURE DISCONTINUATION OF THE STUDY OR PREMATURE CLOSE-OUT OF A SITE

The sponsor may discontinue the study or close-out a site in some cases e.g.;

- If the information on the product leads to doubt as to the benefit/risk ratio;
- If the Investigator has received from the Sponsor all Investigational Product, means and information necessary to perform the Clinical Trial and has not included any patient after a reasonable period of time mutually agreed upon;
- If results of interim analysis show a statistically significant difference between placebo and active arms (in favor of active arm), the study will be terminated for the benefit of patients who were randomly assigned to placebo arm and to rapidly disseminate evidence supporting a treatment benefit to the broader community;
- If the aim of the Clinical Trial has become outdated or is no longer of interest;
- In the event of breach by the Investigator of a fundamental obligation under this agreement, including but not limited to breach of the Clinical Trial Protocol, breach of the applicable laws and regulations or breach of the ICH guidelines for Good Clinical Practice.

In any case, the Sponsor will inform the appropriate Ethics Committee(s) (IRB/IEC) and Health Authorities. In addition, investigators should be notified by written notice.

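### The sample-size text states a one-sided 5% test, which needs about 34 patients per arm; the stated 43 belongs to a two-sided 5% test, and no analysis section says which side applies

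*Protocol*

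**What the plan says.** Section 16.1 of the protocol, with the same text in the synopsis, sets out the calculation "with an alpha error of 5% using one-sided 95% CI of" a Mann–Whitney test, with 80% power and "an effect size between placebo and lowest active dose of 0.63, a sample of 43 patients for each arm will be required". An allowance of 10% for drop-out takes this to 47 per arm and 141 in total. A footnote cites Gpower 3.1 as the software. The parent distribution is not named.

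Section 16.4.2 says "All tests will be performed on the 5% level of significance" and names no side.

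The interim rule appears twice. Section 16.4.5 reads "If a statistically significant difference is observed between placebo and active arm(s), the study will be terminated". Section 19 makes stopping depend on "a statistically significant difference between placebo and active arms (in favor of active arm". Neither gives a side or an alpha. The one-sided wording of the sample-size paragraph is thus the only statement of side in the protocol.

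**The concern.** The paragraph gives every input needed to check the sample size except the parent distribution, and 43 looks too large for a one-sided 5% test at this effect size. Either the side is misstated or the power is.

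The side sets the critical value: about 1.645 for a one-sided 5% test and 1.960 for a two-sided 5% test, in large samples. A comparison in Heptex's favour with a one-sided p-value between 0.025 and 0.05 is significant on one reading and not on the other. That decides the final claim. It also decides the interim, where a significant difference ends the trial. The protocol should leave no doubt about this before anyone sees unblinded results.

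**Working it through.** **Inputs from the protocol.** Alpha 0.05, one-sided; power 0.80; effect size d = 0.63; Mann–Whitney test; 43 per arm; drop-out 10% (all section 16.1). Allocation is 1:1:1 (section 10.1), so each dose is compared with placebo 1:1.

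**Assumption.** The protocol does not state the method behind the Mann–Whitney figure. I used the asymptotic relative efficiency (ARE) method, with a normal parent first and other parents as a range.

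**Formula.** With n per arm, the noncentrality is d × √(n × ARE / 2) and the degrees of freedom are 2 × n × ARE − 2. Power is the probability that a noncentral t variable exceeds the critical t value. For a normal parent, ARE = 3/π = 0.955.

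**Can 43 be reproduced from the stated inputs?**

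- n = 33, one-sided 5%: noncentrality 0.63 × √(33 × 0.955 / 2) = 2.501, df 61.0, critical t 1.670, power 79.6%.
- n = 34, one-sided 5%: noncentrality 2.538, df 62.9, critical t 1.669, power 80.7%. The requirement is therefore **34**.
- n = 43, one-sided 5%: noncentrality 2.855, df 80.1, critical t 1.664, power **88.2%**.

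So 43 is not reproduced.

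**With only the side changed.**

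- n = 42, two-sided 5%: noncentrality 2.821, df 78.2, critical t 1.991, power 79.6%.
- n = 43, two-sided 5%: noncentrality 2.855, df 80.1, critical t 1.990, power 80.5%. The requirement is **43**, an exact match. A one-sided 2.5% test uses the same critical value and also gives 43.

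**Other parent distributions and methods** (n per arm for 80% power):

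| Method | One-sided 5% | Two-sided 5% |
|---|---|---|
| Normal parent (ARE 3/π) | 34 | 43 |
| Minimum ARE (0.864) | 37 | 47 |
| Logistic parent | 30 | 37 |
| Laplace parent | 22 | 28 |
| t-test | 32 | 41 |
| Noether's formula | 35 | 45 |

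No one-sided 5% figure exceeds 37.

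**Rounding of the effect size.** Values from 0.625 to 0.635 give 33 to 34 per arm one-sided. To need 43, a one-sided 5% test with a normal parent would require d of about 0.55.

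**Simulation.** Mann–Whitney tests on normal data with a shift of 0.63 SD (20,000 runs) gave, one-sided, 80.5% power at n = 34 and 88.1% at n = 43. Two-sided power at n = 43 was 80.4%.

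**After drop-out.** 47 × 0.9 = 42.3, so about 42 evaluable per arm. With a normal parent, power is then 87.5% one-sided and 79.6% two-sided.

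**The case against.** The arithmetic is not in dispute, but four objections deserve an answer.

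**The cause is not proved.** A one-sided 5% error divided over the two dose comparisons would be one-sided 2.5% each, which also gives 43. On that reading the side is correct and the level is what is missing. This is possible, but the protocol mentions no such split. It affects how the correction is worded, not whether one is needed: the paragraph as written still does not yield 43.

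**Nothing is lost in sample size.** This stands. With a normal parent, 43 per arm is more than the stated one-sided test needs and just enough for a two-sided one. The exception is the least favourable parent (minimum ARE), where two-sided power at 43 is 76.4%.

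**Analysis detail may sit in the statistical analysis plan.** Silence about the side in section 16.4 would not be a fault on its own. But the protocol does state a side, and that side conflicts with its own sample size. A plan using two-sided 5% would contradict the only side the protocol gives. A plan using one-sided 5% would leave the 80% power figure wrong.

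**The interim wording shows no conflict.** This is fair. Stopping only in the active arms' favour is compatible with either side. Sections 16.4.5 and 19 show only that the question is not settled there.

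**Conclusion.** The point holds. The stated inputs give 34 per arm with a normal parent (22 to 37 over the four parents tried), not 43, and power at 43 would be 88.2%. Changing the test to two-sided 5%, or equivalently to one-sided 2.5%, gives exactly 43 with 80.5% power. The exact match rests on the ARE method and a normal parent; the finding that one-sided 5% does not reach 43 holds for every variant tried.

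The practical consequence is an unfixed error rate, not a shortage of patients: 5% or 2.5% per test in Heptex's favour, at both the interim and the final analysis. It should be corrected. What the sponsor actually entered in the software cannot be known from the protocol.

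**What to change.** Check the settings of the original calculation, then make the text match.

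- If it was two-sided 5% (or one-sided 2.5% per comparison), replace the one-sided 95% wording in section 16.1 and the synopsis with that level and side, and name the normal parent distribution. This reproduces 43.
- If a one-sided 5% test is truly intended, say so in section 16.4 and restate the power at 43 per arm as about 88%.

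In either case, give the same side and level in section 16.4 and its synopsis copy, and in both statements of the interim rule (sections 16.4.5 and 19).

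The cost is wording only. Enrolment stays at 47 per arm and 141 in total. With about 42 evaluable per arm after 10% loss, two-sided power is 79.6% with a normal parent, in effect the 80% planned.

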16.2 ANALYSIS POPULATIONS

The obtained clinical data will be analyzed on an intention-to-treat basis. Primary analysis will be done by intention-to-treat including all eligible enrolled patients with at least one treatment dose and post first dose assessment (ALT & AST) attending any post treatment visit and efficacy variables will be analyzed using the last-observation-carried-forward convention (LOCF).

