11 CONCOMITANT MEDICATIONS

Throughout the study, investigators may prescribe any concomitant medications or treatments deemed necessary to provide adequate supportive care except other liver support, hepatoprotective medications and any medications prohibited as per the eligibility criteria. If these are required, the participant will be withdrawn. Any medication, other than the study medication taken during the study will be recorded in the CRF.

Any medication or vaccine (including over-the-counter or prescription medicines, vitamins and/or herbal supplements) that the subject is receiving during participation in the study must be recorded in the electronic case report form. The investigator should review all concomitant medications for any potential interactions. During the Post-Treatment Period, all medications will be collected.

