16.3 STUDY ENDPOINTS

During interim analysis (at 6 months of treatment) and final analysis at the end of treatment, the following endpoints will be evaluated:

16.3.1 Primary Efficacy Endpoint:

- Compare the mean relative change in ALT & AST levels between the experimental arms and the control arm.
- Compare proportions of patients with normal ALT & AST at end of treatment between the experimental arms and the control arm. The cut-off values of ALT were 0-43 IU/L and of AST were 0-40 IU/L⁷.

16.3.2 Secondary Efficacy Endpoints:

- Comparing the mean change in Fib-4 score between the experimental arms and the control arm.
- Comparing the frequency and percentage of patients experiencing hepatic complications

⁶ Gpower 3.1

⁷ Uslusoy H, Nak S, Gülten M, Bıyıklı Z. Non-alcoholic steatohepatitis with normal aminotransferase values. World Journal of Gastroenterology. 2009;15(15):1863.

between the experimental arms and control arm.

16.3.3 Exploratory Endpoint:

- Compare the mean relative change in lipid profile levels between the experimental arms and the control arm.

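### Section 16.2 fixes LOCF for the primary efficacy analysis, so an early leaver's enzyme value stands in for week 36; Section 16.4.2 names a different patient set, which may leave LOCF little to act on

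*Protocol*

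**What the plan says.** Protocol Section 16.2 defines the primary set: "Primary analysis will be done by intention-to-treat including all eligible enrolled patients with at least one treatment dose and post first dose assessment" of ALT and AST at any later visit. For that set, "efficacy variables will be analyzed using the last-observation-carried-forward convention (LOCF". This is a fixed rule, not something left open.

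The primary endpoints refer to the end of treatment. Section 16.4.2 compares "The mean relative change in ALT & AST levels between the experimental arms and the control arm from baseline till end of treatment", and Section 16.3.1 adds the normalisation endpoint: "Compare proportions of patients with normal ALT & AST at end of treatment between the experimental arms and the control arm". Under the assessment schedule (Section 2), ALT and AST are taken at screening and at weeks 8, 12, 24 and 36.

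Section 16.4.2 gives the change analysis a different set. It "will be done on eligible population of patients without protocol violation and who have at least one treatment dose and an evaluable primary endpoint". The normalisation analysis uses a similar set, worded as free of protocol deviation. Section 16.4.2 also says: "Procedure for accounting for missing, unused, and spurious data will be explained in the statistical analysis plan".

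On leaving, Section 11 says of prohibited drugs, including other liver support and hepatoprotective medication: "If these are required, the participant will be withdrawn". Section 18 allows discontinuation for disease progression, among other reasons. After withdrawal it describes only follow-up of adverse events.

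**The concern.** LOCF assumes that ALT and AST stay where they were at the last visit. A patient last sampled at week 8 is scored at week 36 with a value 28 weeks old. Someone whose enzymes were normal at week 12 counts as normal at the end of treatment, whatever happened next.

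The assumption is least credible in the patients it is applied to, since needing a liver drug and disease progression are both grounds for leaving. With no enzyme sample described after withdrawal, the trial cannot check it.

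Both primary endpoints are exposed. So is the interim look: Section 16.3 evaluates the same endpoints at 6 months, and Section 16.4.5 ends the study on a significant difference. A carried-forward week 8 or 12 value could feed that decision.

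**Working it through.** **Plan's own figure.** Section 16.1 uses effect size 0.63, 80% power and 5% alpha with a Mann–Whitney test, and concludes that "a sample of 43 patients for each arm will be required plus an expected drop-out rate of 10" per cent. Take the noncentral t with Mann–Whitney efficiency 0.955: effective size m = 0.955n, noncentrality 0.63 × √(m/2). A two-sided 5% test gives n = 43 (power 80.5%). The one-sided test described in the text gives 34. So 43 reproduces, but only as two-sided; this does not affect the present point. Adding 10%: 43 × 1.1 = 47.3, stated as 47.

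**How many values are carried forward.** 47 × 0.10 = 4.7 patients per arm. This is an upper figure, because the 16.2 set omits leavers with no post-dose ALT and AST.

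**Effect on the ALT difference.** Section 16.1 gives a change of −20 U/L on placebo and, as the improvement sought, double that (−40) on active. Let dA and dP be drop-out on active and placebo, and k the share of the week 36 change that leavers had reached at their last visit.

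LOCF difference = −40 × [(1 − dA) + k·dA] + 20 × [(1 − dP) + k·dP]

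Three possible targets are shown. All are assumptions, since the protocol gives no enzyme data after withdrawal.
- *Continued*: leavers would have matched completers. Difference = −20.
- *Effect lost*: active leavers end at the placebo mean. Difference = −40(1 − dA) − 20dA + 20.
- *Baseline*: all leavers return to zero change. Difference = −40(1 − dA) + 20(1 − dP).

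Percentages show how far LOCF is too large (+) or too small (−).

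| Drop-out active / placebo | k | LOCF | Continued | Effect lost | Baseline |
|---|---|---|---|---|---|
| 10% / 10% | 1 | −20.0 | −20 (0%) | −18 (+11%) | −18 (+11%) |
| 10% / 10% | 0.5 | −19.0 | −20 (−5%) | −18 (+6%) | −18 (+6%) |
| 20% / 20% | 1 | −20.0 | −20 (0%) | −16 (+25%) | −16 (+25%) |
| 20% / 20% | 0.5 | −18.0 | −20 (−10%) | −16 (+12.5%) | −16 (+12.5%) |
| 20% / 5% | 1 | −20.0 | −20 (0%) | −16 (+25%) | −13 (+54%) |
| 20% / 5% | 0.5 | −16.5 | −20 (−17.5%) | −16 (+3%) | −13 (+27%) |
| 10% / 20% | 1 | −20.0 | −20 (0%) | −18 (+11%) | −20 (0%) |

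The same LOCF result can be too small for one target and too large for another.

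**No drug effect.** Suppose both arms drift by −20 U/L and leavers had reached a quarter of that (−5). The LOCF difference is 15 × (dA − dP): 0 at equal drop-out, 15 × 0.15 = 2.25 U/L at 20% vs 5%, and 15 × 0.20 = 3.0 U/L at 30% vs 10%. It counts against the arm with more drop-out. With SD 20/0.63 = 31.7 U/L, 47 per arm and a two-sided 5% t-test, 20,000 simulated trials gave type I error of 5.2% at 10% in both arms, 6.1% at 20% vs 5% and 7.1% at 30% vs 10%.

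**Normalisation.** Assume 30% to 50% of leavers were normal at their last visit but would not be at week 36. At 10% drop-out LOCF adds 0.10 × 30% to 0.10 × 50% = 3 to 5 percentage points in an arm, or 1.4 to 2.4 of 47 patients.

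**Standard error.** 31.7 × √(2/47) = 6.55 U/L, against 31.7 × √(2/42.3) = 6.90 U/L if only completers counted, a gap of about 5%.

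**The two sets.** Section 16.2 keeps a leaver who has one post-dose sample and fills in week 36. Section 16.4.2 drops anyone with a protocol violation and requires an evaluable endpoint. If evaluable means measured at the end of treatment, most leavers are excluded and LOCF has almost nothing to fill.

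**The case against.** The strongest defence is that the effect at the planned 10% drop-out is small and of uncertain sign, in a phase II trial whose objectives are exploratory. That stands: at equal 10% drop-out the simulated type I error is essentially nominal.

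Four stronger readings are tempting, and the documents do not support them.

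- **LOCF favours Heptex.** LOCF applies to placebo leavers too. If the effect is still building when patients leave, it works against the arm that loses more of them.
- **The 11% and 25% figures are the gain from a mixed model.** They are not. They assume that leavers had reached the full change and then lost it. A mixed model assuming data are missing at random would predict completer-like week 36 values for such leavers and also give about 20 U/L. The gap lies between two definitions of the effect. The 20% drop-out rate is also not the plan's.
- **Section 16.4.2 contradicts LOCF by sending missing-data procedures to the SAP.** That sentence defers detail. It neither withdraws LOCF nor conflicts with it.
- **LOCF clearly understates the standard error.** Each patient contributes one value that was really measured, so the standard error is right for a last-observation endpoint. The 5% gap only compares 47 with 42.3 patients.

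The figures above are also in absolute U/L, whereas the endpoint is relative change, so they are indicative only.

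None of this rescues LOCF as the primary method. A bias of unknown sign, tied to the reasons for leaving, is still a defect when the visits needed for a better analysis are already scheduled.

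**Conclusion.** The point holds as a should-fix. Section 16.2 fixes a rule that treats week 8, 12 or 24 values as week 36 values in patients whose leaving is linked to outcome. The size rests on the assumed targets, the −20 and −40 U/L of Section 16.1, and how far leavers had improved. Over the scenarios shown, the error at 10% drop-out in both arms runs from 5% too small to 11% too large. At 20% vs 5% it runs from 17.5% too small to 54% too large. These percentages illustrate the assumptions and do not predict the trial's bias.

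Whether LOCF operates at all depends on which set governs. Sections 16.2 and 16.4.2 both claim the primary analysis and cannot both hold. This is the contradiction that needs settling.

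**What to change.** 1. Name one primary set, the intention-to-treat set of Section 16.2, in both sections and in the synopsis. Keep the set without protocol violations as supportive.
2. Replace LOCF as the primary method with a mixed model for repeated measures, fitted to log ALT and separately to log AST at weeks 8, 12, 24 and 36. Terms: baseline, arm, visit and arm-by-visit; read the week 36 contrast of each dose with placebo. Using the log ratio to baseline keeps the relative-change scale. The screening sample is the only pre-dose value in the schedule and would serve as baseline.
3. For normalisation, count a missing week 36 value as not normal.
4. Keep LOCF as a sensitivity analysis.
5. State whether the intended effect includes loss of effect after stopping. If it does, add return-to-baseline multiple imputation, because the mixed model does not address that question.

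The cost is protocol and SAP wording and slightly more programming; steps 1 to 4 need no new visits. The mixed model replaces the planned t-test or Mann–Whitney test for the change endpoint and relies on missing at random, which the data cannot confirm. Counting missing as not normal penalises the arm with more drop-out, so drop-out should be reported by arm beside it.
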